8.5 Recording of Adverse Events

If the patient has experienced adverse event(s), the investigator will record the following information in the CRF:

- The nature of the event(s) will be described by the investigator in precise standard medical terminology (i.e. not necessarily the exact words used by the patient).
- The duration of the event will be described in terms of event onset date and event ended data.
- The intensity of the adverse event: Mild/Moderate/Severe according to Common Terminology Criteria for Adverse Events version 4.0 (CTCAE).
- The Causal relationship of the event to the study medication will be assessed as one of the following:

Unrelated:

There is not a temporal relationship to investigational product administration (too early, or late, or investigational product not taken), or there is a reasonable causal relationship between non-investigational product, concurrent disease, or circumstance and the AE.

Unlikely:

There is a temporal relationship to investigational product administration, but there is not a reasonable causal relationship between the investigational product and the AE.

Possible:

There is reasonable causal relationship between the investigational product and the AE. Dechallenge information is lacking or unclear.

Probable:

There is a reasonable causal relationship between the investigational product and the AE. The event responds to dechallenge. Rechallenge is not required.

Definite:

There is a reasonable causal relationship between the investigational product and the AE.

- Action taken
- The outcome of the adverse event – whether the event is resolved or still ongoing.

8.6 Reporting Procedure

8.6.1 AEs and SAEs

All adverse events and serious adverse events that should be reported as defined in section 8.1.1 will be recorded in the patient's CRF.

SAEs must be reported by the site investigator to the sponsor represented by the coordinating investigators within 24 hours after the site has gained knowledge of the SAE. Every SAE must be documented by the investigator on the SAE pages (to be found as part of the CRF). The Serious Adverse Event Report Form must be completed and signed. The initial report shall promptly be followed by detailed, written reports if necessary. The initial and follow-up reports shall identify the trial subjects by unique code numbers assigned to the latter.

The coordinating investigators keep detailed records of all SAEs reported and perform an evaluation with respect to seriousness, causality and expectedness.

8.6.2 SUSARs

SUSARs will be reported to the Competent Authority according to national regulation. The following timelines should be followed:

On suspicion of SUSAR the site investigator report to the sponsor represented by the coordinating investigators. If the coordinating investigators consider the event as a SUSAR they report it to the Department of clinical research support. Personell at the department of clinical research support, not otherwise involved in the trial, will unblind the treatment and ensure that all relevant information about SUSARs that are fatal or life-threatening is recorded and reported unblinded as soon as possible to the Competent Authority, no later than seven days after knowledge of such a case, and that relevant follow-up information is subsequently communicated within an additional eight days.

All other SUSARs will be reported to the Competent Authority concerned and to the Ethics Committee concerned as soon as possible but within a maximum of 15 days of first knowledge.

SUSARs will be reported using the CIOMS form.

8.6.3 Annual Safety Report

Once a year throughout the clinical trial, the sponsor will provide the Competent Authority with an annual safety report. The format will comply with national requirements.

8.6.4 Clinical Study Report

The adverse events and serious adverse events occurring during the study will be discussed in the safety evaluation part of the Clinical Study Report.

8.7 Procedures in Case of Emergency

The site investigators are responsible for assuring that there are procedures and expertise available to cope with emergencies during the study. Code break may be relevant in case of toxicity and other events were knowledge of treatmentarm matters for further management of the patient. Envelopes with randomization codes are available in such cases.

9 DATA MANAGEMENT AND MONITORING

9.1 Case Report Forms (CRFs)

The designated investigator staff will enter the data required by the protocol into an electronic Case Report Form (CRF). The site investigators are responsible for assuring that data entered into the CRF is complete, accurate, and that entry is performed in a timely manner. The signature of the investigator will attest the accuracy of the data on each CRF. If any assessments are omitted, the reason for such omissions will be noted on the CRFs. Corrections, with the reason for the corrections will also be recorded.

9.2 Source Data

The medical records for each patient should contain information which is important for the patient's safety and continued care, and to fulfill the requirement that critical study data should be verifiable.

To achieve this, the medical records of each patient should clearly describe:

- That the patient is participating in the study, e.g. by including the enrollment number and the study code or other study identification;
- Date when Informed Consent was obtained from the patient and statement that patient received a copy of the signed and dated Informed Consent;
- Results of all assessments confirming a patient's eligibility for the study;
- Diseases (past and current; both the disease studied and others, as relevant);
- Treatments withdrawn/withheld due to participation in the study;
- Results of assessments performed during the study;
- Treatments given, changes in treatments during the study and the time points for the changes;
- Visits to the clinic / telephone contacts during the study, including those for study purposes only;
- Non-Serious Adverse Events and Serious Adverse Events (if any) including causality assessments;
- Date of, and reason for, discontinuation from study treatment;
- Date of, and reason for, withdrawal from study;
- Date of death and cause of death, if available;
- Additional information according to local regulations and practice.

9.3 Study Monitoring

We plan a strategic monitoring with focus on the most critical data, such as primary endpoint data and key safety data, including adverse events and a higher source document verification (SDV) coverage on the first one or two subjects enrolled at each site in order to establish an early data quality "yardstick" for each site. A risk-based monitoring plan will be made.

Monitors, and/or competent authorities will be allowed access to source data for SDV in which case a review of those parts of the hospital records relevant to the study may be required.

9.4 Confidentiality

The investigator shall arrange for the secure retention of the patient identification and the code list. Patient files shall be kept for the maximum period of time permitted by each hospital. The study documentation (CRFs, Site File etc) shall be retained and stored during the study and for 15 years after study closure. All information concerning the study will be stored in a safe place inaccessible to unauthorized personnel.

9.5 Database management

The Department of clinical research support, OUS, will perform data management in accordance with ICH guidelines, CRS SOPs, and described in the trial specific Data Handling Plan. The plan will describe the processes and documentation related to data capture and data quality control. The data will be captured in an electronic CRF (eCRF). The eCRF will ensure security (to prevent unauthorized access to, or loss of data) and storage during trial. After database lock, the trial will be archived by sponsor and removed from the eCRF.

10 STATISTICAL METHODS AND DATA ANALYSIS

10.1 Determination of Sample Size ** [name]?

In a previous trial on well-characterized LNB patients, 102 patients were treated with either oral doxycycline or IV cephtriazone for two weeks. From this trial we have available outcome scores at 12 months from 93 patients, measured on a slightly different composite clinical scale, but with the same max score of 64. We consider the scales as so similar that the results from the former trial can be used in power analyses in the current planned trial. The mean score in the former trial was 1.7 with a standard deviation (SD) of 2.6.

10.2 Randomization

10.2.1 Allocation- sequence generation

Computerized allocation to two or six weeks doxycycline (1:1) will be performed at Department of clinical research support, OUS by an internet based solution. Automatic e-mails with the result of the randomization will be sent to the involved hospitals.

10.2.2 Blinding and emergency unblinding

To achieve maximum objective performance and reporting of the study we will use the “penta blind” approach. First, we use the traditional double blind design with blinding of participants and investigators (first and second blinding). The staff evaluating end-points and adverse effects is blinded to all other study information (third blinding). Then the content of all tables and figures are fixed before any study data are available (fourth blinding) and then the statistical procedures are performed with treatment groups marked as group A and B. First, when all the tables and figures are filled out, the randomization code is broken. Unblinding for the investigator will be done when all patients have completed the six month visit (primary and several secondary end-points answered), and for the patients after the 12 month registration. Emergency unblinding is permissible as described in section 8.7. Unblindingprocedure in case of SUSAR is described in section 8.6.2.

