2.2 Secondary Endpoints

Improvement of composite clinical score from inclusion to 12 months after end of treatment defined as clinical score at inclusion minus clinical score at 12 months. (Table1)

Fatigue Severity Scale (FSS) at six and 12 months after end of treatment. FSS is translated and validated for Norwegian purposes (12). It measures level of agreement (1– 7) with nine statements. The final score represents the mean value of the nine items. Severe fatigue is defined as a score >5 in a Norwegian population. Reported mean score in 20 American

healthy adults is 2.3 (13), and reported mean score in 50 Norwegian patients treated for LNB is 3.5 versus 2.1 in the control group (3).

Patient Health Questionnaire (PHQ-15) at six months. PHQ-15 is a brief, validated questionnaire, which consists of 13 questions concerning severity of different subjective somatic symptoms the last 4 weeks, and 2 questions concerning sleep and tiredness. Each item is scored from 0 to 2, and sum score ranges from 0 to 30. Sum scores of 5, 10, and 15 represent cutpoints for low, medium, and high symptom severity, respectively (27).

Short Form-36 (SF-36): SF-36 is a valid and reliable questionnaire assessing health related quality of life. It consists of 36 questions concerning general health perceptions, physical functioning, physical role functioning, emotional role functioning, social role functioning, bodily pain, vitality and mental health. A Norwegian normal material exist (28).

CSF findings at six and 12 months: Cell count, IgG index, OCB's, and *Bb* antibodies

Other laboratory tests, MRI, and neuropsychological assessments: In a subset of patients at inclusion and six months after end of treatment (WP4 of BorrSci).

Safety as measured by serious adverse events and less serious side effects of treatment (Table 3)

Table 3. Safety measures

Treatmentweek	0	1	2	3	4	5	6	7-10
Nausea		x	x	x	x	x	x	x
Vomiting		x	x	x	x	x	x	x
Diarrhea		x	x	x	x	x	x	x
Skin reactions		x	x	x	x	x	x	x
Vaginitis		x	x	x	x	x	x	x
Blodtests (Hb, Hb, white blood cell count with differential, platelet count, ASAT, ALAT, GT, ALP, Creatinine)	x		x		x			
Other AE or complications		x	x	x	x	x	x	x

Secondary and exploratory objectives and their endpoints and assessments are detailed in WP 3 and 4 (Appendix A)

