6.2.6 Twelve months After End of Treatment (Follow-up)

- Interview about symptom description, concomitant medication, and sick leave attributable to LNB
- Composite clinical score
- FSS, PHQ-15
- Laboratory analyses
 - Blood: Hb, white blood cell count with differential, platelet count, ASAT, ALAT, GT, ALP, Creatinine, CRP, electrophoresis, Bb antibodies, TBE antibodies
 - CSF: Cellcount, protein level, Oligoclonal bands, Bb antibodies,
 - In addition aliquots of specimens will be transferred for biobank storage

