10.4 Planned analyses

The main statistical analysis is planned when all patients have completed the six months visit. Deviation from the original statistical plan will be described and justified in the Clinical Study Report. Amendments to plan can be done until day of database lock.

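### Section 10.2.2 allows the investigator to be unblinded while some 12-month composite scores are still to be rated, and does not secure the blinding of the 12-month raters

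*Combined protocol and SAP*

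**What the plan says.** Section 10.2.2 gives two unblinding times. For the investigator: "Unblinding for the investigator will be done when all patients have completed the six month visit". For the patients, it is after the 12-month registration. Section 10.4 places the main analysis at the same six-month point.

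Section 2.2 lists as a secondary endpoint: "Improvement of composite clinical score from inclusion to 12 months after end of treatment". Section 6.2.6 schedules the "Composite clinical score" at the 12-month visit and names no rater.

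Section 10.2.2 counts participants and investigators as the first and second blinding. It then adds a third: "The staff evaluating end-points and adverse effects is blinded to all other study information (third blinding"). It sets no end date for this third layer and does not say whether its members are separate from the investigators. The opening of section 8 makes the site and coordinating investigators responsible for detecting and documenting adverse events, and section 8.5 has the investigator record them. Evaluating adverse effects is also one of the two tasks of the third-layer staff.

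**The concern.** Patients enrolled in roughly the last six months of recruitment reach their 12-month visit after the point at which the investigator may learn the allocation. If the same person rates the score, these ratings are made with knowledge of the arm and are pooled with blinded ratings from earlier patients.

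The score leaves room for judgement. Section 2.1 grades each item 0, 1 or 2 by its influence on daily life and counts it only if it is considered related to the neuroborreliosis. Section 7.1 concedes that the score is not validated and says it was simplified partly to reduce disagreement between raters. The items most open to the rater are the examiner's findings; symptoms reported by patients who remain blinded are less exposed. At stake is the 12-month comparison, which shows whether the six-month answer lasts.

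**Working it through.** The plan gives no figure for this point, so there is nothing to reproduce. The arithmetic below gives scale only.

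**Inputs from the document.** Recruitment 01.10.15 to 31.12.19 (section 3), which is 50.99 months. Treatment lasts six weeks (section 5.3). 120 patients, 60 per arm (section 4.2). The earlier trial's score had mean 1.7 and SD 2.6 (section 10.1).

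**Assumptions.** The accrual pattern, the delay from the last six-month visit to the code break, and the size of any rating shift are not in the document. No dropout is assumed; dropout would lower the counts.

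**Calendar.** A patient enrolled on 31.12.19 ends treatment on 11.02.20, so the last six-month visit is about 11.08.20. The 12-month visits still outstanding are those of patients enrolled in the last six months.

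**Exposed patients** = monthly accrual × (6 − delay in months).

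| Assumed accrual | Rate per month | No delay | 2 months | 4 months |
|---|---|---|---|---|
| Uniform | 120/50.99 = 2.353 | 14.1 (11.8%) | 9.4 | 4.7 |
| Linear rise from zero during 2016, then constant | 120/(6 + 35.94) = 2.861 | 17.2 (14.3%) | 11.4 | 5.7 |
| All in 2017–2019 | 120/35.94 = 3.339 | 20.0 (16.7%) | 13.4 | 6.7 |

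The second row reflects section 3, where the other centres join gradually in 2016. The figure of 20 is not a ceiling. Under otherwise uniform accrual, if the last six months (184 of 1,553 days) run at half or double pace, the count at zero delay is 120 × 92/1,461 = 7.6 or 120 × 368/1,737 = 25.4.

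**Effect on the 12-month difference.** Suppose a between-arm rating shift applies to the exposed patients only. The overall difference then moves by (exposed/120) × shift. The standard error is 2.6 × √(2/60) = 0.475. This borrows the earlier trial's SD of the score, because the SD of improvement is not given.

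- No delay, 14.1 exposed: shifts of 0.25, 0.5 and 1 point give 0.029, 0.059 and 0.118 points (0.06, 0.12 and 0.25 SE).
- No delay, 20.0 exposed: 0.042, 0.083 and 0.167 points (0.09, 0.18 and 0.35 SE).
- Two-month delay, 9.4 to 13.4 exposed: from 9.4/120 × 0.25 = 0.02 to 13.4/120 × 1 = 0.11 points (0.04 to 0.24 SE).
- Four-month delay, 4.7 to 6.7 exposed: from 0.01 to 0.06 points (0.02 to 0.12 SE).

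For comparison, a shift of 1 point is 1/1.7 = 59% of the earlier trial's mean score.

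**The case against.** The strongest reply is that section 10.2.2 already separates the roles. It counts investigators as one layer and endpoint staff as another, and a third layer made up of the same people would add little. It gives unblinding times only for the investigator and the patients, so the natural reading is that the endpoint staff stay blinded. It also leaves undefined whether the investigator means the site or the coordinating investigators. This stands in part: it makes the exposure conditional. It does not remove it, because separation and duration are nowhere stated and section 8 gives investigators an overlapping task. Reading the term as the lead investigator alone does not settle the matter either, since the synopsis lists the lead hospital among the centres.

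A second reply is that the timing is a deliberate choice, made when the primary endpoint is complete. That is true, and it is why the matter is small.

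A third is that zero delay is the least plausible case, because the code opens only after the tables are completed: "First, when all the tables and figures are filled out, the randomization code is broken". This also stands; the delayed columns are the more realistic ones.

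A reader might further infer that the masked analysis of the 12-month data is unprotected, since 12-month tables cannot be filled at six months and section 10.4 says "Amendments to plan can be done until day of database lock" without mentioning a separate 12-month lock. The document does not support a defect here. With the main analysis set at six months, the tables in question can be read as the six-month ones. Under the fourth layer, "the content of all tables and figures are fixed before any study data are available (fourth blinding"), and section 10.4 adds: "Deviation from the original statistical plan will be described and justified in the Clinical Study Report". At most this calls for a clarifying sentence.

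**Conclusion.** The gap is real but conditional. Under the rule as written, 12-month ratings in the last-recruited patients can be made by someone who knows the allocation, and nothing in the document excludes it. A reader might infer that these ratings will be unblinded. The text does not show that: it happens only if the raters are investigators who receive patient-level codes.

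The effect is small. The six-month primary endpoint is untouched, patients stay blinded to 12 months, and section 1.1 describes remaining objective findings as rarer than subjective complaints. Exposure is about 14 of 120 patients with uniform accrual and no delay (17 to 20 under the other two patterns tabulated), about 9 to 13 with a two-month delay and 5 to 7 with a four-month delay. The illustrative shifts of 0.25 to 1 point amount to 0.06 to 0.35 SE at zero delay and to less with a delay. These shifts are assumptions. It would be wrong to treat 1 point as an upper bound, because nothing in the document limits how far an unblinded rater could move the score.

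**What to change.** Amend section 10.2.2 so that group-level six-month results may be released on time, while patient-level allocation stays sealed from site and coordinating investigators, and from anyone rating patients, until the last 12-month visit is entered and locked. Keep the emergency and SUSAR unblinding in sections 8.7 and 8.6.2 as exceptions. If the raters are already separate from the investigators, a sentence saying so, and that they stay blinded to individual allocation until the last 12-month visit, would meet the main point.

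The cost is mostly wording. Investigators wait about six months longer for patient-level codes. Personnel without patient contact must hold the code and produce the group-level report. Section 8.6.2 already names uninvolved staff who can unblind, but only for SUSARs, so the wider role would have to be agreed. No visit is added and the six-month report is not delayed.

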10.3 Population for Analysis

The following populations will be considered for the analyses:

- Intention to treat (ITT) population: All randomized participant, regardless of protocol adherence.
- Per-protocol population (PP): Includes all without significant protocol deviation
- Safety population: Includes all subjects who have received at least one dose of study medication. Subjects who withdraw from the study will be included in the safety analysis. A list of withdrawn subjects, preferably with the reasons for withdrawal, will be made.

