3 OVERALL STUDY DESIGN

The study is a phase Phase III, randomized, penta-blind, placebo-controlled, multicenter trial with a non-inferiority design. The trial will be conducted and reported according to the CONSORT statement (Consolidated Standards of Reporting Trials), the SPIRIT initiative (Standard Protocol Items: Recommendations for Interventional Trials), and Good Clinical Practice (GCP) standards, and registered in ClinicalTrials.gov

Study Period	Estimated date of first patient enrolled: 01.10.15 (startup at Sørlandet Hospital 2015, recruitment from other centres gradually during 2016)
	Anticipated recruitment period: 01.10.15 - 31.12.19
	Estimated date of last patient completed: 31.12.20
Treatment Duration:	Six weeks
Follow-up:	13 months

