5 TREATMENT

For this study, doxycycline and placebo are defined as Investigational Medicinal Product (IMP).

Included patients will be randomized to two weeks treatment with oral doxycycline (200 mg once daily) followed by four weeks placebo or six weeks treatment with oral doxycycline (200 mg once daily).

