5.1 Drug Identity, Supply and Storage

IMPs (active drug and placebo) will be produced at Kragerø Tabletproduksjon. Production documentation is described in a separate document (Appendix B). All included patients will receive active drug (doxycycline) for 14 days, thereafter half of them will receive placebo and the other half will receive active drug (doxycycline) for four weeks.

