5.6 Drug Accountability

The responsible site personnel will confirm receipt of study drug and will use the study drug only within the framework of this clinical study and in accordance with this protocol. Distribution and return of the study drug will be documented in the drug accountability log and in the CRFs.

If patients are included in the study after already having started doxycycline 200 mg per day, the responsible site personnel will ensure that the appropriate amount of capsules, depending on the number of days already treated, are removed from the study drug packaging before distribution to the patients. The amount of study drug delivered to the patients will be documented in the CRF.

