10.5 Statistical Analysis **[name]?

Results will be reported as mean scores with standard deviation or proportions as appropriate.

To compare the two groups on the primary outcome, we will use a general linear model with treatment group was factor and adjust for duration of symptoms, gender and age. The analysis will be conducted according to the intention to treat principle.

For other analysis, comparison between groups will be done with e.g. independent samples t-test, nonparametric Mann-Whitney-U test or Pearsons chi-square test for crosstabs as appropriate.

P-values <0.05 are considered statistically significant.

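### The only analysis named for the non-inferiority endpoint keeps patients who stop while both arms still take the same drug; add a supportive set of patients who reach the point where the arms diverge

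*Combined protocol and SAP*

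**What the plan says.** Section 3 describes a "penta-blind, placebo-controlled, multicenter trial with a non-inferiority design". Section 5 states: "Included patients will be randomized to two weeks treatment with oral doxycycline", followed by placebo, or to six weeks of doxycycline. Section 10.2.1 gives no day for the allocation, but the flow chart in 6.1 marks a single delivery of study drug, at baseline. Allocation at inclusion is therefore the natural reading.

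Section 5.1 fixes where the arms part: "All included patients will receive active drug (doxycycline) for 14 days, thereafter half of them will receive placebo", while the other half continues on doxycycline. On blinding, 10.2.2 says "we use the traditional double blind design with blinding of participants and investigators". Section 5.6 also provides for the case "If patients are included in the study after already having started doxycycline 200 mg per day"; for these patients the identical period after randomisation is shorter than 14 days.

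Section 10.3 defines the "Intention to treat (ITT) population: All randomized participant, regardless of protocol adherence", together with a per-protocol and a safety set. For the primary model, 10.5 says: "The analysis will be conducted according to the intention to treat principle". No analysis is assigned to the per-protocol set.

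On follow-up after stopping, 6.3 lets a patient leave assessments as well as treatment, 6.4.1 asks for a final assessment only where it can be obtained, and 6.2.4 makes the withdrawal visit voluntary. Only patients who leave before treatment starts are replaced. No rule for a missing six-month score is given.

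**The concern.** A patient who stops before completing 14 days of doxycycline has received nothing that differs between the arms. Apart from a code break, neither patient nor investigator knows the arm, so the decision to stop should not depend on it. The expected arm difference among such patients is zero, and including them moves the overall difference toward zero on average. In a superiority trial that is conservative. In a non-inferiority trial it works in favour of the claim.

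Early stops are foreseeable. Section 4.3 concedes that the diagnosis may be uncertain at inclusion, 6.3 lists incorrect enrolment, safety and voluntary withdrawal as reasons to discontinue, and the one scheduled contact to look for such reasons falls on days 6 to 8.

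The design offers an unusual remedy. Because the first phase is identical and blinded, leaving out patients who stop in it essentially preserves the randomised comparison. The per-protocol set does not have this property, since it can exclude patients for events after the arms diverge.

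**Working it through.** **The plan's own figure.** The sample size of 120 (60 per arm, section 4.2) cannot be reproduced. Section 10.1 stops after a mean of 1.7 and an SD of 2.6, with no margin, power or dropout allowance. That SD belongs to a 12-month score on a slightly different scale, not to improvement at six months. Section 10.5 gives 0.05 without saying whether it is one- or two-sided.

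**Assumptions.** One-sided 2.5% error; SD 2.6; 60 per arm; a margin M that this size would fit at a true difference of zero; a share p in each arm that stops before divergence.

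- SE = 2.6 × √(2/60) = 0.475.
- M at 80% power = (1.96 + 0.84) × 0.475 = 1.33.
- M at 90% power = (1.96 + 1.28) × 0.475 = 1.54.

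**Dilution.** Let D be the true difference (six weeks minus two weeks, in mean improvement) among patients who reach divergence. If all early stoppers are scored, the expected ITT difference is (1-p) × D + p × 0 = (1-p) × D.

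**Effect on the claim.** Non-inferiority is claimed when the estimate plus 1.96 × SE lies below M. With D = M, the probability of a claim is Φ((M - (1-p)M)/SE - 1.96) = Φ(p × M/SE - 1.96). At 80% power M/SE = 2.80.

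| p (assumed) | Expected ITT difference, M = 1.33 | Claim rate, M = 1.33 | Claim rate, M = 1.54 |
|---|---|---|---|
| 5% | 1.26 | Φ(-1.82) = 3.4% | 3.6% |
| 10% | 1.20 | Φ(-1.68) = 4.6% | 5.1% |
| 15% | 1.13 | Φ(-1.54) = 6.2% | 7.0% |

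Analysing only patients who reach divergence keeps the rate at 2.5%.

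**Dependence on scoring.** If no early stopper has a six-month score and the model uses complete cases, there is no dilution. If p = 10% and half of the stoppers are scored, they form 5/95 = 5.3% of the analysed patients. M/SE becomes 2.80 × √0.95 = 2.73, and the rate is Φ(0.053 × 2.73 - 1.96), about 3.5%.

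**Single trials.** In a simulation with p = 10%, adding the stoppers moved the estimate away from zero in about 20% of trials when D = 1.33 and in about 45% when D = 0.

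**Stoppers who do worse.** If they score 5 points worse in both arms, the wider interval offsets part of the effect: 4.0% instead of 4.6% at p = 10%.

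**Power of the restricted set.** At D = 0 and p = 10%: Φ(2.80 × √0.90 - 1.96) = Φ(0.70), about 76%, against 80%.

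**The case against.** The strongest objection concerns the target. If the margin is meant for the effect of assigning a duration to every included patient, which the primary objective can be read to ask, the ITT error stays nominal and nothing is inflated. This stands: the figures above apply only when the margin is read as a difference among patients who reach divergence. A reader might infer that ITT is wrong here, and the documents do not support that.

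Two further inferences are also too strong. One is that early stoppers can only pull the result toward zero; this is true in expectation, and the simulation shows frequent exceptions. The other is that 10.5 counts every early stopper; sections 6.2.4, 6.3 and 6.4.1 do not secure a six-month score, and a patient who withdraws consent is the least likely to have one.

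The illustration is also generic. Because M was solved from the sample size, SD and n cancel and the rate depends only on 2.80 × p. Nothing in the documents shows that p is 5% to 15%. It may be small: under 8.3, progression mostly counts only after 14 days of treatment, and an absent antibody finding does not by itself end eligibility under 4.3.

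Finally, it can be said that the per-protocol set already covers these patients. It might exclude them, but its criterion is loose, it can also exclude for events after divergence, and no analysis uses it.

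A practical objection stands in part. Diaries and pill counts are collected only at the end of week 10, after the arms have diverged, so a set built on them alone could depend on the arm. Code breaks are possible under 8.7. The fix allows for both.

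**Conclusion.** The concern holds as a gap in sensitivity, not as an error in ITT. Patients who stop before the arms diverge and are scored at six months carry no information on two versus six weeks. In expectation they shrink the difference by 1-p in the direction that favours non-inferiority, and the plan has no analysis that shows how much this matters.

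The size cannot be determined from the documents. The illustrated rise from 2.5% to between 3.4% and 6.2% rests on an assumed p of 5% to 15%, an assumed margin of 1.33, one-sided 2.5% testing, a score for every stopper, and a margin defined among patients who reach divergence. With few early stops, or few of them scored, the effect is small or absent. The change is still worth making because it is cheap and the restricted comparison remains essentially randomised.

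**What to change.** - **Section 10.3:** add a set of all randomised patients not recorded as having stopped study drug before completing 14 days of doxycycline, counting days taken before inclusion, analysed in the arm to which they were randomised.
- **Membership:** base it on the dated discontinuation record in the CRF and the day 6 to 8 contact, with the diary as support. Keep patients with a missing diary in the set. List any code break before divergence. Fix membership before the code is broken.
- **Section 10.5:** keep ITT as the primary analysis. State that the same model is also run on this set as a supportive analysis, and that a non-inferiority conclusion from ITT is described as robust only if this analysis agrees.

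Section 10.4 allows changes to the plan until database lock, but 10.2.2 fixes the content of tables before study data are available, so the addition belongs in the plan now.

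The cost is one definition and one extra model run on data already collected. The set is slightly smaller than ITT and has somewhat lower power, about 76% instead of 80% at p = 10% under the assumptions above.
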